2.3.2 Animal model data

Preclinical genetic dMMR mouse models and dMMR patient-derived xenografts were developed in the laboratory of [name] in Einstein. In order to generate mice with tissue-specific inactivation of MSH2 called VCMsh2^{loxP}, Cre-LoxP recombination was used to target MSH2 loss to the intestinal mucosa of Msh2^{loxP} mice using a Villincre transgene. Patient tumor cells were injected subcutaneously into the right flank side. All VCMsh2^{loxP} mice spontaneously developed intestinal adenocarcinomas 6-8 months after the inoculation and died 4-6 weeks after diagnosis in the absence of treatment. Rapamycin was injected subcutaneously 3-5 times per week into tumor-

[figure not shown]
bearing VCMsh2^{loxP} mice. Treatment response was assessed by micro PET-CT at 14 days of treatment and tumor volume measured using the 6"/150 mm Vernier caliper W/fin adj. (Geneva Gage, INC)

In the absence of treatment, dMMR xenografts and pMMR mice evidenced increases in tumor volume and in mean standardized uptake values measured by micro PET-CT at day 14. When rapamycin was administered, all treated tumors (n>100) showed complete regression after 2-3 weeks of treatment and no tumor re-growth was observed in dMMR xenografts (Figure 2); while the tumor continued to increase in pMMR mice (Figure 3 and 4).

[figure not shown]

mTOR inhibitors, including rapamycin and analogs, have a well-established cytostatic effect. In addition, a **cytotoxic effect can be exerted in dMMR xenografts as a consequence of higher levels of oxidative stress** generated by Akt hyperactivation and failure to repair the resulting oxidative DNA damage in dMMR tumor cells. mTOR inhibition by rapamycin leads to Akt activation by phosphorylation to pAkt. FOXO transcription factors, including FOXO3a, promote resistance to oxidative stress by induction of antioxidant enzymes. pAkt induces phosphorylation of FOXO3a leading to its inhibition. (Figure 5, A and B). This leads to accumulation of ROS levels

as evidenced by 8-oxoG a common DNA lesion resulting from ROS leading to autophagy and cell death as evidenced by Beclin-1 expression (Figure 5 C).

To show that cell death resulting from inability to repair oxidative DNA damage was restricted to dMMR cell lines; we performed experiments with two cell lines: HT29 (pMMR) and LOVO (dMMRI). These showed that pAkt and pFOXO3a and ROS levels increase in dMMR and pMMR cell lines treated with rapamycin; but, 8-oxoG levels increase only in dMMR cell lines. To show the role of pAkt in cell death; experiments adding an Akt inhibitor (Akti) and N-acetylcysteine (an antioxidant) were perfomed, showing that 8oxoG levels do not increase when dMMR cell lines are treated with concomitant rapamycin and Akti or with rapamycin and NAC (Figure 6D). Cell viability is reduced in dMMR cell lines treated with rapamycin; however, the cytotoxic effect is attenuated when Akti or NAC are added (Figure 6E).

2.3.3 Safety Data

Sirolimus was FDA-approved in 2010 for the prevention of organ rejection in patients receiving kidney transplants after proving superiority to azathioprine in this setting. Additionally, it was FDA-approved in 2015 for the management of lymphangioleiomyomatosis after showing improvement in lung function in a randomized clinical trial.

A pilot study that included 4 patients (gastric cancer:3, and cholangiocarcinoma:1) assessed the safety and efficacy of rapamycin among patients with refractory solid tumors with PIK3CA amplification/mutation. In this study, sirolimus was administered at 1 mg daily in 28-day cycles. Two patients received 2 cycles and one patient each received 1 and 4 cycles, respectively. Dose reductions/modifications were not required, grade 3 or greater were not observed and there were no treatment-related deaths. Three patients had stable disease (SD) after one cycle and one patient had SD after 4 cycles

2.4 Clinical experience with mTOR inhibitors

In the United States, there are three FDA approved mTOR inhibitors. Of these, 2 of them (everolimus and temsirolimus) have been approved in the treatment of cancer and for organ transplantation rejection prophylaxis in kidney recipients; while the other (sirolimus) has been approved for the latter indication. In general, the most common adverse events are rash, asthenia, and mucositis. Common laboratory abnormalities include anemia, hyperglycemia, hyperlipidemia, and hypertriglyceridemia.

Temsirolimus was FDA-approved for the treatment of patients with advanced renal cell carcinoma (RCC) in 2007 after a randomized clinical trial showed superiority of the combination of temsirolimus and interferon versus interferon alone. Everolimus is FDA-approved for the treatment of patients with advanced renal cell carcinoma refractory, neuroendocrine tumors of gastrointestinal, pancreatic or lung origin, renal angiomyolipoma, tuberous sclerosis, subependymal giant cell astrocytoma and postmenopausal women with metastatic, hormone-positive breast cancer in the second-line setting. Sirolimus was FDA-approved in 2010 for the prevention of organ rejection in patients receiving kidney transplants after proving superiority to azathioprine in this setting. Additionally, it was FDA-approved in 2015 for the management of lymphangioleiomyomatosis after showing improvement in lung function in a randomized clinical trial.

A pilot study that included 4 patients (gastric cancer:3 and cholangiocarcinoma:1) assessed the safety and efficacy of rapamycin among patients with refractory solid tumors with PIK3CA amplification/mutation. In this study, sirolimus was administered at 1 mg daily in 28-day cycles. Two patients received 2 cycles and one patient each received 1 and 4 cycles, respectively. Dose reductions/modifications were not required, grade 3 or greater were not observed and there were no treatment-related deaths. Three patients had stable disease (SD) after one cycle and one patient had SD after 4 cycles (9).

2.5 Relevance and Significance

Despite exciting therapeutic improvement in dMMR metastatic solid tumors, effective treatment options after immunotherapy remain scarce. This study is relevant, as it will evaluate a potentially effective drug targeted to this patient population. This clinical trial has bench-to-bedside translational potential that could provide the foundation for an entirely new therapeutic option for patients with dMMR solid tumors that have run out of other options.

Currently, multiple clinical trials are evaluating the efficacy of mTOR inhibitors alone or in combination for the treatment of different cancer types (10-15); however, none of them have selected dMMR tumors. Therefore, this proposal is highly innovative, as it will focus the intervention to a subgroup of patients that is more likely to benefit, as suggested by our pre-clinical data. Furthermore, the evaluation of tissue biomarkers will confirm whether sirolimus can exert a cytotoxic effect (which has never been reported before) limited to dMMR tumors.

3. OBJECTIVES

3.1 Primary objective:

 To evaluate the efficacy of sirolimus by estimating the overall response rate (ORR) as assessed by Response Evaluation Criteria In Solid Tumors versión 1.1 (RECIST v1.1) in patients with metastatic dMMR solid cancer after immunotherapy (either due to disease progression or to inability to tolerate treatment).

3.2 Secondary objectives:

- To assess potential tissue biomarkers (Akt, pAkt, FOXO3a, pFOXO3a, 80xoG expression by immunohistochemistry, tumor mutational burden/gene mutations by next-generation sequencing), the effect of sirolimus treatment on these biomarkers, and possible correlation between these biomarkers and clinical response.
- To evaluate other clinical end-points such as progression-free survival, response duration and overall survival of sirolimus in patients with metastatic dMMR solid cancer after immunotherapy (either due to disease progression or to inability to tolerate treatment).
- To evaluate tolerability and safety of sirolimus using Common Terminology
 Criteria for Adverse Events (CTCAE) grading scale.

4. MATERIAL AND METHODS

4.1 Study design

Open-label, single arm, phase II clinical trial among patients with metastatic, dMMR solid tumors refractory/unable to tolerate immunotherapy.

4.2 Patient selection

4.2.1 Inclusion criteria

- Metastatic solid cancer tumor after immunotherapy (either due to progression of disease or inability to tolerate treatment)
- dMMR by immunohistochemistry (IHC) defined as the loss of expression in any of the four major MMR proteins (MLH1, MSH2, MSH6 and PMS2) or by next-generation sequencing (NGS)
- Age older than 18 at the time of informed consent
- Eastern Cooperative Oncology Group performance status of 0-2
- ≥1 measurable lesion based on RECIST, version 1.1 (16)
- Absolute neutrophil count (ANC) ≥1,500 mm3
- Platelet count ≥75,000 mm3
- Hemoglobin ≥ 9 g/dl
- Aspartate aminotransferase (AST) ≤3.0 times the upper normal limit(UNL)
- Alanine aminotransferase (ALT) ≤3.0 times the upper normal limit (UNL)

- Bilirubin ≤1.5 times the UNL
- Serum creatinine ≤1.5 times the UNL

4.2.2 Exclusion criteria

- Received immunotherapy in the prior 21 days.
- Have not recovered from toxicities of prior treatments to at least grade 1.
- Symptomatic central nervous system (CNS) metastases
- Pregnancy or Breast-feeding.

4.4 Dosing delays/modifications

Each participant will be evaluated in the oncology cancer center by a physician every 2 weeks for the first 2 cycles and on the first day of each subsequent cycle. The evaluation will include history and physical. Laboratory parameters including cell blood count (CBC), basic metabolic panel (BMP) and liver tests will be checked in every encounter to determine dosing delay/modification. Each cycle is of 28 days in duration starting once therapeutic trough sirolimus levels are achieved in blood.

Side effects will be evaluated using the National Cancer Institute Common Terminology Criteria for Adverse Events, version 4.0. Dose delay and modifications will be required for thrombocytopenia (<75K), neutropenia (ANC<1), or any persistent non-hematologic grade 2 or 3 toxicity. Discontinuation of sirolimus will be required for any grade 4 toxicity, or any toxicity requiring treatment interruption for ≥ 1 cycle.

4.5 Response Evaluation Plan

Each participant will be required to have a recent imaging (CT or PET-CT) within 21 days of treatment initiation which will be considered as baseline. In C1D1, the patient will be assessed in the oncology clinic to document baseline symptoms and laboratory exams including CBC, BMP, liver tests will be performed and repeated at everyvisit.

Imaging (CT or PET-CT) within 21 days of treatment initiation will be considered as baseline. Response to treatment will be assessed by imaging (CT-CAP or PET-CT) after after 8 weeks of achieving therapeutic sirolimus levels, and every 8 weeks thereafter. Images will be reviewed by the radiology team based on RECIST v1.1 criteria (16).

4.6 Biomarker studies

4.6.1 Prior to treatment initiation:

- Historical tumor samples will be requested for all participants for evaluation of potential biomarkers. In cases where archival biopsies are not available, the patient will be offered a biopsy prior to treatment initiation. This will be optional and will not affect enrollment into the clinical trial. These samples will be used to evaluate the baseline expression of Akt, pAkt, FOXO3a, pFOXO3a, 80xoG expression will be evaluated by immunohistochemistry in the laboratory of [name].
- We anticipate that most of the patients would have had next-generation sequencing requested before our evaluation, so, the results will be directly requested. In cases where it was not done; it will be ordered. This will be used to

explore potential mutations that could correlate with treatment response.

4.6.2 During treatment:

• Repeated biopsies after 8 weeks of treatment will be offered to all participants that had an evaluable biopsy prior to treatment initiation. This will be optional and will not affect continuation into the clinical trial. Changes in the expression of Akt, pAkt, FOXO3a, pFOXO3a, 80xoG expression will be evaluated by immunohistochemistry in the laboratory of [name].

5. STATISTICAL CONSIDERATIONS

5.1 Endpoints

5.1.1 Primary Endpoint

 Objective response rate (ORR) defined as the proportion of patients who achieve a complete response (disappearance of all target tumors) or a partial response (≥30% decrease in the sum of the longest diameters of target tumors) based on RECIST V1.1 (16).

5.1.2 Secondary Endpoints

- Progression free survival (PFS): PFS is defined as the time from treatment initiation to progression of known metastases or new metastatic site, or death from any cause after a timeframe of 24 weeks.
- Response duration (RD): RD is defined as time from documentation of tumor response to disease progression.
- Overall survival (OS): OS is defined as the time from treatment initiation to death from any cause.

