5.2 Sample size

This study is designed as a single arm, single-stage phase II trial to test the null hypothesis that Ho: ORR \leq 0.05 vs H_A: ORR > 0.05. The target sample size of 16 subjects was determined assuming that the true ORR = 25% with sirolimus, i.e. an absolute improvement in ORR of 20%. If the number of responses at the end of the trial is 3 or more out of 16, we will conclude that sirolimus is beneficial for patients with dMMR tumors and further studies of this treatment will be conducted. If the drug is actually not effective (ORR \leq 0.05), there is a 5% probability of erroneously concluding that it is effective (Type I error rate). If the drug is truly effective (ORR \geq 0.25), there is at least 80% probability of correctly concluding that it is (power). To account for a 15% drop-out rate, 19 patients will be enrolled. Because of the limited total sample

size, this trial is designed as a single stage study that does not allow for early stopping due to lack of efficacy.

[figure not shown]
We anticipate that it will be feasible to enroll 19 participants in a 10-month period based on the patient load treated at Montefiore/Einstein Cancer Center and the commitment of collaborators from other cancer centers in New York City (Lincoln Hospital, Jacobi Medical Center, St. Barnabas hospital, Cornell Cancer Center) to refer eligible patients for this trial. This study will be funded by the Montefiore/Einstein Cancer Center

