5.3 Analysis Plan

The ORR will be estimated as the proportion of patients with metastatic dMMR solid cancer refractory to immunotherapy who achieved the endpoint of objective response after treatment with sirolimus. Corresponding exact 95% confidence intervals will also be computed for the true ORR. The distribution of progression-free survival and overall survival will be estimated using the Kaplan-Meier method. Greenwood's method will be applied to estimate confidence intervals.

As a secondary aim, we will evaluate other clinical efficacy end-points such as PFS (time from target serum sirolimus levels to progression of known metastases or new metastatic site, or death from any cause), response duration (time from documentation of tumor response to disease progression.) and overall survival (OS, time from target serum sirolimus levels to death from any cause). The distribution of PFS, DR and OS will be estimated using the Kaplan-Meier method. Greenwood's method will be applied to estimate confidence intervals.

Provided the number of patients who achieve objective response is sufficient, exploratory analyses to assess the association between ORR and the expression of tissue biomarkers will be performed. An exact test for trend for ordered contingency tables will be used to compare the frequency of subjects with low, moderate and high biomarker expression between patients with and without objective response; Fisher's exact test will be used to compare the frequency of subjects that had an increase in biomarker expression after treatment between patients with and without objective response. Gene mutations will be reported as frequencies and compared between patients with and without objective response by Fisher's exact test. The two sample Wilcoxon rank sum or T-test will be conducted to compare the tumor mutational burden between patients with and without objective response.

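### Response duration ends only at disease progression, so under Kaplan-Meier a responder who dies without documented progression would be censored and the reported duration could be overstated

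*Combined protocol and SAP*

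**What the plan says.** Response duration is a secondary objective (section 3.2) and a secondary endpoint. Section 5.1.2 states: "RD is defined as time from documentation of tumor response to disease progression". Section 5.3 gives the same rule: "response duration (time from documentation of tumor response to disease progression". The estimator is set in section 5.3: "The distribution of PFS, DR and OS will be estimated using the Kaplan-Meier method".

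PFS is handled differently. In section 5.1.2 its events are "progression of known metastases or new metastatic site, or death from any cause after a timeframe of 24 weeks", and section 5.3 also counts death from any cause. (The reference to 24 weeks is a separate matter.) OS counts all deaths.

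Response imaging comes after "8 weeks of achieving therapeutic sirolimus levels, and every 8 weeks thereafter" (section 4.5). Section 4.3 ties the end of treatment to progression shown on imaging. No section gives a censoring rule for response duration, treats death as a competing event, or says that a death counts as progression.

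**The concern.** The definition leaves no place for a responder who dies with no progression on record. The death could be from progression that no scan had yet shown, from toxicity, or from another cause. Kaplan-Meier with progression as the only event can only censor that patient, and then assumes the same future risk of progression as in responders still under follow-up. That is hard to defend in metastatic cancer after immunotherapy with ECOG status 0-2 and scans 8 weeks apart, where a death between scans may itself be unrecorded progression.

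At stake is the description of how long responses last. With few responders, readers will look to duration to judge what the responses are worth, and a single patient can move the estimate.

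**Working it through.** **1. How many responders there would be.** The plan states no figure for response duration, so the design figures serve only to fix the number of patients in this analysis. From section 5.2: "The target sample size of 16 subjects was determined assuming that the true ORR = 25% with sirolimus", the null rate is 5%, and the success rule is "If the number of responses at the end of the trial is 3 or more out of 16".

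- Exact binomial, 16 patients, at least 3 responses: type I error 0.0429 at ORR 5%; power 0.803 at ORR 25%.
- Enrolment: 16/0.85 = 18.8, rounded up to 19.
- The design reproduces. Expected responders at 25%: 0.25 × 16 = 4 (0.25 × 19 = 4.75 if all enrolled patients count). At the null: 0.05 × 16 = 0.8.

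**2. Direction.** Take the patient as leaving the risk set on the date of death under either definition. Counting the death multiplies the curve by one further factor below 1; censoring omits that factor. The curve with deaths censored is therefore never below the curve with deaths counted. If the patient were instead censored at the last scan before death, the curve could dip slightly between that scan and the death, but it is still the higher one from the death onward.

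**3. General size.** Assume constant hazards, p for progression and d for death without progression, independent of each other. Then s = d/(p + d).

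- Median with death counted: ln 2/(p + d).
- Median with death censored: ln 2/p.
- Ratio: (p + d)/p = 1/(1 - s).

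The documents give no value for s, so a range is shown:

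| s (assumed) | Overstatement of the median |
|---|---|
| 5% | 1/0.95 = 1.05 |
| 10% | 1/0.90 = 1.11 |
| 20% | 1/0.80 = 1.25 |
| 30% | 1/0.70 = 1.43 |

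If each of four responders independently has probability s of such a death, the chance of at least one is 1 - (1 - s)^4: 19% at 5%, 34% at 10%, 59% at 20%.

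**4. Small-sample example (all times assumed).** Four responders, weeks counted from response: death without documented progression at 12, progressions at 16 and 24, one response ongoing at 30.

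| Week | As written (death censored) | Death counted |
|---|---|---|
| 12 | 1 | 3/4 = 0.75 |
| 16 | 2/3 = 0.67 | 3/4 × 2/3 = 0.50 |
| 24 | 2/3 × 1/2 = 0.33 | 0.50 × 1/2 = 0.25 |

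As written, the median is 24 weeks. With death counted the curve lies at exactly 0.50 from week 16 to week 24. The median is then 16 weeks if taken as the first time at or below 0.5, or (16 + 24)/2 = 20 weeks by the midpoint convention. The shift is 8 or 4 weeks.

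**5. When the median does not move.** Assume instead four responses ending at weeks 8, 16, 24 and 32. If all endings count, the curve is 0.75, 0.50, 0.25, 0, and the median is 16 weeks (midpoint 20).

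- Ending at week 8 or 16 is a censored death: median 24 under both conventions.
- Ending at week 24 is a censored death: median still 16 by the first-time rule. The curve stays at 0.50 from week 16 to week 32, so the midpoint rises to (16 + 32)/2 = 24.
- Ending at week 32 is a censored death: median unchanged under both conventions; only the tail is higher (0.25 instead of 0 at week 32).

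**The case against.** The strongest case against runs as follows.

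- *The plan never says that deaths are censored.* True; a reader should not report it as a stated rule. It follows from a progression-only event analysed by Kaplan-Meier, and nothing elsewhere in the document offers another route.
- *The bias may never appear.* True. It needs at least one responder to die without documented progression, and the documents give no rate.
- *Sampling error swamps it.* In the example, Greenwood 95% limits at week 16 are 0.67 ± 1.96 × 0.27 (about 0.13 to 1.00, capped) as written and 0.50 ± 1.96 × 0.25 (about 0.01 to 0.99) with death counted. This stands as a reason not to lean on the median under either definition. It does not excuse an error whose direction is known beforehand.
- *No decision depends on response duration.* True. Section 5.2 rests the conclusion on the response count alone, and duration has no hypothesis, threshold or comparator. The pembrolizumab responses of more than 6 months in section 2.1 are background, not a benchmark; medians of 16, 20 and 24 weeks all fall short of 6 months, so that comparison would not change in the example.
- *Deaths are visible elsewhere.* PFS in section 5.3 and OS count them, and section 4.4 has patients seen every 2 weeks for two cycles and then at the start of each cycle. This softens the problem, but the response duration curve itself stays uncorrected, and the protocol is silent on unscheduled imaging.
- *Time to progression among responders is a legitimate measure.* It is, if labelled as such and analysed with death as a competing event. The plan does neither.

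**Conclusion.** The point holds in conditional form. The rule in sections 5.1.2 and 5.3, followed as written, would censor a responder's death without documented progression. If that happens, the curve from the death onward is too high and the reported duration could be too long.

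The size cannot be taken from the documents. The factors of 1.05 to 1.43 rest on an assumed s of 5% to 30% and on constant, independent hazards. The shift of 8 or 4 weeks rests on four assumed response times with the death placed early, and on the choice of median convention.

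A reader might infer that duration will certainly be overstated, that one death always moves the median by 8 weeks, or that the trial's efficacy conclusion is in doubt. The documents support none of these: such a death may not occur, a late one may leave the median unchanged, and the ORR test, the rule of 3 responses in 16 and the sample size do not use response duration. This is a defect in a descriptive secondary endpoint, worth correcting because the fix is simple and the direction of error is known.

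**What to change.** In sections 5.1.2 and 5.3, define response duration as the time from first documented CR or PR to the earlier of RECIST v1.1 progression or death from any cause. Add that responders with neither are censored at their last adequate tumour assessment. State which median convention will be used, since with about four responders it can change the figure.

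If a progression-only measure is really wanted, say so, name it accordingly, and estimate it by cumulative incidence with death as a competing event.

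The cost is one clause and one censoring sentence in two places. Deaths are already needed for PFS and OS, so no new data or patients are required and no design figure changes. The downside is that reported duration may be shorter. The change should be made before responders' outcomes are known, so that the choice cannot be influenced by them.
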